9.4. ALTERNATIVES TO PARTICIPATION

Subjects who do not participate in this study will receive the current standard of care for radiation dermatitis at the University of Rochester Medical Center. Study participation is voluntary. Subjects can choose to not to take part or withdraw from the study at any time, for whatever reason.

10. SAFETY AND REPORTABLE EVENTS

10.1. ADVERSE EVENT MONITORING

This is a safety study to determine if Silverlon® dressing can be indicated for radiation dermatitis. The primary outcome is not clinical response to treatment; it is safety (i.e., adverse reactions/events/complications). Any adverse event will be documented on the AE Source Doc throughout the course of the study. Any safety information for an individual patient that is volunteered by a study subject during the course of this research must be reported as described below:

All adverse events, whether observed by the Investigator radiation oncologist, or nurse, elicited from, or volunteered by the subject, will be documented. Each adverse event will be recorded on the electronic AE Source Doc. This form will record the will include a brief description of the experience, the date of onset, the date of resolution, the duration and type of experience, the severity, contributing factors, and any actions taken. This description will be in the summary not during a subject's regularly scheduled clinic appointment.

Adverse event (AE): is any untoward medical occurrence in a subject using study device, and which does not necessarily have a causal relationship with this treatment. An adverse event can be any unfavorable and unintended sign (including abnormal laboratory test results), symptom, or disease temporally associated with the use of the study device, whether or not considered related to the study device. The relationship of each adverse event to the study device must be recorded as one of the choices on the scale described below.

Attribution: An assessment of the relationship between the adverse event and the protocol treatment, using the following categories.

ATTRIBUTION	DESCRIPTION
Unrelated	The AE is clearly NOT related to treatment.
Unlikely	The AE is doubtfully related to treatment.
Possible	The AE may be related to treatment.
Probable	The AE is likely related to treatment.
Definite	The AE is clearly related to treatment

Page 30 of 41 RSRB STUDY00004587 Version Date: 09/14/2021 NCT04238728 **Hospitalization (or prolongation of hospitalization):** For AE reporting purposes, a hospitalization is defined as an inpatient hospital stay equal to or greater than 24 hours. **Life Threatening Adverse Event:** Any AE that places the subject at immediate risk of death from the AE as it occurred.

Serious Adverse Event (SAE): Any adverse event occurring at any dose that results in **ANY** of the following outcomes:

- Death
- A life-threatening adverse event
- Inpatient hospitalization or prolongation of existing hospitalization (for \geq 24 hours).
- A persistent or significant incapacity or substantial disruption of the ability to conduct normal life functions.
- A congenital anomaly/birth defect.
- Important Medical Events (IME) that may not result in death, be life threatening, or require hospitalization may be considered a serious when, based upon medical judgment, they may jeopardize the subject and may require medical or surgical intervention to prevent one of the outcomes listed in this definition.

10.2. RECORDING ADVERSE EVENTS

Study personnel will assess adverse events by recording all voluntary complaints of the subject. Any side effects and adverse reactions will be noted on the AE Source Doc. Study personnel will check with the nurse and/or treating radiation oncologist regarding any reported adverse reactions. All adverse events, whether observed by the Investigator, the treating radiation oncologist, or volunteered by the subject, will be documented. Adverse events will be reported per the University of Rochester Research Subjects Review Board (RSRB) reporting requirements. Each adverse event will include a brief description of the experience, the date of onset, the severity of the event, the relationship to investigational intervention, and any action taken with respect to the study and intervention. Adverse event monitoring will occur at the start of informed consent until completion of the study.

The relationship to the study device and the severity of each adverse event (i.e., attribution) as judged by the investigator or radiation oncologist must also be recorded. An adverse event is any untoward medical occurrence in a subject administered study device, and which does not necessarily have a causal relationship with this treatment. The relationship of each adverse event to the study device must be recorded as one of the choices on the scale below:

DEFINITE: Causal relationship is certain (e.g., the temporal relationship between device use and the adverse event onset/course is reasonable; there is a clinically compatible response to dechallenge; other causes have been eliminated; and the event must be definitive pharmacologically or phenomenologically using a satisfactory re-challenge procedure, if necessary).

PROBABLE: High degree of certainty for causal relationship (e.g., the temporal relationship between device use and the adverse event onset/course is reasonable; there is a clinically compatible response to de-challenge [re-challenge is not required]; and other causes have been eliminated or are unlikely).

Page 31 of 41 RSRB STUDY00004587 Version Date: 09/14/2021 NCT04238728 POSSIBLE: Causal relationship is uncertain (e.g., the temporal relationship between device use and the adverse event onset/course is reasonable or unknown; de-challenge/re-challenge information is either unknown or equivocal; and while other potential causes may or may not exist, a causal relationship to study device does not appear probable).

UNLIKELY: Not reasonably related, although a causal relationship cannot be ruled out (e.g., while the temporal relationship between device use and the adverse event onset/course does not preclude causality, there is a clear alternate cause that is more likely to have caused the adverse event than the study device).

UNRELATED: No possible relationship (e.g., the temporal relationship between device use and the adverse event onset/course is unreasonable or incompatible, or a causal relationship to the device is not plausible).

10.3. REPORTING SERIOUS ADVERSE EVENTS

Serious adverse events (SAEs), while a subject is enrolled in the study until the subject completes the study, will be reported in writing to the University RSRB as per their requirements. A serious event refers to any event in which the outcome results in any of the following: death, a life-threatening adverse device experience, inpatient hospitalization or prolongation of existing hospitalization, a persistent or significant disability, incapacity, or a congenital anomaly/birth defect. Important medical events that may not result in death, be life-threatening, or require hospitalization, may be considered a serious adverse experience when, based upon appropriate medical judgment, they may jeopardize the subject and may require medical or surgical intervention to prevent one of the outcomes listed in this definition. Hospitalizations scheduled for an elective procedure or for treatment of a pre-existing condition that has not worsened during participation in the study, will not be considered serious adverse events. The onset date, resolution date, treatment, and outcome of each adverse event will be reported to the Research Subjects Review Board (RSRB) and to the Safety Coordinator using the MedWatch Form FDA 3500A-Mandatory Reporting. Unanticipated problems that involve risks to subjects or others (UPIRTSO) will be reported to the University RSRB and Sponsor.

IRB: As described above, on-study adverse reactions are reported to the University of Rochester Research Subjects Review Board (RSRB). Modifications to the protocol will be reviewed by RSRB before implementation. The RSRB also provides initial and continuing review of study conduct and consent.

Research staff (i.e., PI, Co-investigators, or study coordinator): Will also conduct continuous review of data and subject safety. The review will include for each treatment arm/dose level: the number of subjects, adverse reactions, and responses observed. The Investigator will submit summaries of this data to the Data Safety Monitoring Committee for review as required in the study's protocol review committee approval letter.

11. DATA AND SAFETY MONITORING PLAN

[name] (co-investigator) in Radiation Oncology at University of Rochester will serve as the Clinical Monitor for this study. Approval of protocol, informed consent

Page 32 of 41 RSRB STUDY00004587 Version Date: 09/14/2021 NCT04238728 procedures, and recruitment will be obtained from the University RSRB. Any safety concerns about the clinical protocol will be brought to the immediate attention of the Principal Investigator and Co-investigator. Study personnel will follow aforementioned reporting procedures for adverse event reporting, including any serious adverse events. Protocol deviations and quality issues will be recorded and reported to the IRB per local policies. Remedial and/or corrective action to prevent reoccurrence of protocol deviations or quality issues will be instituted as necessary. Because this study's procedures pose relatively low risk to subjects, monthly data and procedural reviews by the Clinical Monitor and Investigator in consultation with study personnel will be sufficient to identify and ameliorate any potential safety issues. As such, an additional Data and Safety Monitoring Plan document will be not be created for this study.

Patients will have their radiated sites examined once a week by either a radiation oncologist as part of their regular course of radiation therapy. At this examination, any adverse events related to their skin will be recorded. For the purpose of this study, an adverse event will be defined as severe radiation dermatitis meeting the definition of RTOG score grade 4 or above (ulceration, hemorrhage or necrosis) or other adverse reaction of Grade 3 or higher in the area of radiation area where Silverlon® dressing is applied. Patients meeting the definition of 'adverse event' will be withdrawn from the study and the radiation dermatitis then treated according to local protocol as ordered by the attending radiation oncologist. Changes in dose or scheduling of radiation therapy in response to an adverse event will remain the responsibility of the attending radiation oncologist.

If a patient feels that they are having an adverse event outside of the weekly monitoring schedule, they may contact the study coordinator or principal investigator by phone and an immediate follow-up appointment with the radiation oncologist will be arranged.

12. STUDY MONITORING PLAN – Sponsor

The Sponsor and/or designee will monitor the study over its duration. The Sponsor study monitor, Clinical Research Associate (CRA) will visit the site at appropriate intervals to review investigational data for accuracy and completeness and ensure compliance with the protocol. Medical records/source documents (office, clinic or hospital) will be reviewed for subjects looking for primary end-point events. In cases of all-cause mortality and SAE, the study monitor will perform inspection for pertinent documents and records for these events. The CRA will be assisting the site to resolve any data queries and ensuring that relevant source documents related to study events are being retrieved from the site. The Investigator/site will permit access to such records. Source documentation must be available to substantiate proper informed consent procedures, adherence to protocol procedures, adequate reporting and follow-up of adverse events, accuracy of data collected on case report forms, and study device information. A monitoring visit sign-in log will be maintained at the site. The Investigator, Clinical Monitor, and/or research coordinator will be available for monitoring visits. It is expected that the Investigator will provide the study monitor with a suitable working environment for review of study-related documents.

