9.2. PROTECTION AGAINST RISKS

The study protocol, amendments to the protocol, consent forms, study forms and patient-report forms are reviewed by the responsible IRB, University Research Subjects Review Board (RSRB), prior to implementation. The RSRB also provides continuing review of study conduct and consent.

The research staff (*PI, Co-investigators, study coordinator*) will conduct continuous review of data and subject safety. The review will include the number of subjects, adverse reactions, and responses observed. The Investigator will submit summaries of this data to the Research Subjects Review Board (RSRB) for review as required in the study's protocol review committee approval letter.

Study forms and patient-report forms are either electronic forms through REDCap, excel spreadsheets, or paper forms. All data from paper forms will be entered electronically into REDCap database as it is received from the subjects. All electronically captured data will be securely stored in the secure REDCap database at the University of Rochester Medical Center. To protect the confidentiality of subjects, questionnaires and data collected on each subject will be coded, the form collected will contain a numerical Subject ID and Subject Initials. The forms contain the minimum personal identifiers needed for research. The key list with all Subject IDs will be kept in a locked file. All forms will also be kept in a locked file that is separate from the key list that links the subject name and the code number. When data analyses are completed, the key list and paper forms will be destroyed. The required informed consent will be the only record kept of those subjects who have participated in the research. The Silverlon® dressing that will be studied in this project is not associated with any risks.

Any safety information for an individual patient that is volunteered by a study participant during the course of this research will be documented. All adverse events, whether observed by the Investigator, radiation oncologist, or nurse, elicited from or volunteered by the subject, will be documented and reported as described in §10. Each adverse event will include a brief description of the experience, the date of onset, the date of resolution, the duration and type of experience, the severity, contributing factors, and any actions taken. This description will be in the summary not during a subject's regularly scheduled clinic appointment.

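### Section 11 puts a severity floor on 'adverse event' that contradicts sections 10.1 and 10.2; applied literally, it could keep milder dressing-site reactions out of the primary safety count

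*Combined protocol and SAP*

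**What the plan says.** Section 11 describes the weekly skin examination and says that skin-related events found there are recorded. It then states that, for this study, "an adverse event will be defined as severe radiation dermatitis meeting the definition of RTOG score grade 4 or above", or "other adverse reaction of Grade 3 or higher in the area of radiation area where Silverlon® dressing is applied". The next sentence attaches a consequence: "Patients meeting the definition of 'adverse event' will be withdrawn from the study". Section 7 likewise makes RTOG 4 the point at which dermatitis is reported as an adverse event. It sends allergic reactions to the AE Source Doc without a grade limit.

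Section 10.1 defines an adverse event differently: it "is any untoward medical occurrence in a subject using study device, and which does not necessarily have a causal relationship with this treatment". Section 10.2 adds "All adverse events, whether observed by the Investigator, the treating radiation oncologist, or volunteered by the subject, will be documented". It requires a relationship rating for each event and separately requires side effects and adverse reactions to be entered on the AE Source Doc. Section 9.2 says that all adverse events "will be documented and reported as described in §10", and section 11 itself says "Study personnel will follow aforementioned reporting procedures for adverse event reporting, including any serious adverse events".

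The primary outcome (section 1.3) is the reactions or events that the radiation oncologist rates probably or definitely related to the dressing, taken from the Weekly AE/Chart Review Source Doc. Section 13.2 counts events or reactions at the dressing site and names no grade. Section 13.1 expects none, in 30 fully evaluable subjects and in 36 who start treatment.

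**The concern.** One protocol contains two definitions of the term on which its primary outcome rests, and no sentence ranks them. The section 11 definition follows directly on the instruction for the weekly examination, the visit that feeds the AE form. In section 5.3 that form lists skin changes as a yes/no item, while intensity and relationship are listed with the adverse event. A staff member who took section 11 at its word could note a milder reaction without opening an adverse-event entry. The reaction would then have no relationship rating and could not enter a count that requires one.

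The data are meant to support a 510(k) application, and the plan expects a count of zero. A zero is hard to interpret if the text does not settle which reactions were eligible to be counted.

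**Working it through.** **1. The definitions side by side.** Mild and moderate are taken here as below Grade 3; section 11 names no scale for that grade.

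| Reaction at the dressing site | Sections 10.1/10.2 | Section 11, read literally |
|---|---|---|
| RTOG 4 or above dermatitis | adverse event | adverse event |
| RTOG 3 dermatitis | adverse event | not an adverse event |
| Other reaction, Grade 3 or higher | adverse event | adverse event |
| Allergic reaction below Grade 3 | adverse event | not an adverse event, but section 7 still puts it on the form |
| Other mild or moderate reaction | adverse event | not an adverse event |

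The definitions differ in rows 2, 4 and 5. Section 7 closes row 4.

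**2. Whether a lower-grade reaction would still be attributed.** Five places say that it should be:

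- Section 5.1, weekly visit: the oncologist documents any adverse reaction or event, and staff extract its intensity and its relationship to the dressing.
- Section 5.3: the form's intensity field includes mild and moderate.
- Section 10.2: side effects and adverse reactions go on the AE Source Doc, and section 11 redefines neither term.
- Section 1.3: the outcome covers reactions as well as events.
- Section 13.2: the analysis does the same.

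Section 11's definition and section 7's RTOG 4 sentence point the other way. Loss therefore requires staff to follow section 11 literally.

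**3. Which reactions are exposed.** Under section 10.2 a rating of probable requires that "other causes have been eliminated or are unlikely". Every subject receives radiation, so RTOG 3 dermatitis (row 2) would seldom be rated probable or definite under either definition. The real exposure is row 5: mild or moderate non-allergic reactions.

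**4. What one subject does to the result.** Inputs are n = 30 and n = 36, with two-sided 95% Clopper-Pearson limits (section 13.1).

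For x = 0 the upper limit is 1 − 0.025^(1/n):

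- n = 30: 1 − 0.025^(1/30) = 0.1157; the plan prints 0.116.
- n = 36: 1 − 0.025^(1/36) = 0.0974; the plan prints 0.097.

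The plan's figures reproduce, so the question is what is counted and not the arithmetic.

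For x ≥ 1 the lower limit is the 0.025 quantile of Beta(x, n − x + 1) and the upper limit is the 0.975 quantile of Beta(x + 1, n − x). The counts below are assumed, for scale only:

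| Subjects with a related reaction | Proportion | 95% limits |
|---|---|---|
| 0/36 | 0 | 0 to 9.7% |
| 1/36 | 2.8% | 0.1% to 14.5% |
| 2/36 | 5.6% | 0.7% to 18.7% |
| 0/30 | 0 | 0 to 11.6% |
| 1/30 | 3.3% | 0.1% to 17.2% |

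**5. The unit of the count.** The section 13.1 table labels its primary measure as events per number of patients. A Clopper-Pearson interval applies to a proportion of subjects. Two events in one subject would break that correspondence, so the numerator should be subjects with at least one event.

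**The case against.** The strongest reply is that section 11 was meant as a withdrawal trigger. Its definition is followed at once by withdrawal, with the term in inverted commas, and the paragraph before it keeps the section 10 reporting procedures in force. Taken as a general definition, it would stop a death or hospitalisation unrelated to the skin from being an adverse event, contrary to sections 10.1 and 10.3. The section 5.1 weekly text asks for intensity and relationship for reactions as well as events. Subjects are also asked about reactions every week, and the sponsor's monitor checks source records for primary endpoint events.

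Most of this stands. It shows what was probably intended and makes loss of reactions less likely. It does not remove the conflict: section 11 is worded as a definition for this study, section 7 repeats its dermatitis threshold, and no sentence gives section 10 precedence.

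A reader might also infer that section 11 empties the completer analysis of events, because anyone meeting its definition is withdrawn. The documents do not support treating that as a result of the definition. It follows mainly from the fully evaluable rule in section 3.1 and the withdrawal rules in section 7, and would remain after the wording was corrected. Section 13.2 already plans the all-treated analysis, which retains withdrawn subjects.

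**Conclusion.** The contradiction is explicit and unresolved, and it bears on the primary outcome. Its effect on the count is possible, not established. It depends on staff following section 11 over sections 5.1 and 10.2, and on a probable or definite mild or moderate non-allergic reaction occurring. The documents give no rate for either, so no expected bias can be stated. The intervals above show only how sensitive an expected zero is to one or two subjects.

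Two stronger readings are tempting. One is that lower-grade reactions will be dropped; sections 1.3, 5.1, 5.3, 10.2 and 13.2 all point to recording or counting them. The other is that RTOG 3 dermatitis is the main loss. It would rarely meet the attribution standard. It also remains visible in the RTOG and RISRAS scores and, where it leads to withdrawal, on the Withdrawal Form and in the section 8 stopping rule.

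**What to change.** - State that the section 10.1 definition governs all adverse-event recording and the primary count.
- Relabel the section 11 sentence as a withdrawal or escalation criterion, and the section 7 RTOG 4 sentence as an expedited-reporting criterion.
- Report the primary outcome as the number and percentage of subjects with at least one probable or definite dressing-site reaction of any grade, with a Clopper-Pearson interval, in the all-treated and completer sets already planned.

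The cost is a few sentences of protocol wording. The downside is a few more adverse-event entries and possibly a less favourable safety table.

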13. DATA ANALYSIS AND MONITORING

13.1. Sample Size Justification

The study will recruit 36 total subjects to accrue 30 fully evaluable subjects with an estimated 20% withdrawal rate. The target enrollment table in §3.9 shows that we have access to enough eligible patients to complete this study in 12 months. The following table shows the

Page 33 of 41 RSRB STUDY00004587 Version Date: 09/14/2021 NCT04238728 precision estimates and 95% confidence intervals for our primary objective (i.e., adverse events related to Silverlon®) and secondary objective (i.e., compliance and withdrawal rate). Our estimates for adverse events (primary and intent to treat analyses) are based on published trials showing no reported adverse events or allergic reactions to silver nylon dressing in patients receiving radiation (8, 15-17). Our estimates for the primary objective were conducted with sample size of 30 for the fully evaluable subjects and 36 for all subjects that initiated treatment. Our estimates for compliance (secondary analyses) are based on the Aquinos-Parsons et al study in breast cancer patients that showed a 97% compliance rate for silver nylon dressing (8). Our estimates for compliance were conducted using sample size of 30 for fully evaluable subjects. In subjects that withdraw from the study, we will be able to partially evaluate compliance because of their early termination of treatment and study procedures. Our estimates for withdrawal are based on the Vavassis et al study in head & neck cancer patients using silver nylon dressing that reported 1 of 12 subjects (i.e., 8%) withdrew from the study (17). Our estimates for withdrawal were conducted using a sample size of 36 to capture all subjects that initiated treatment. 95% Exact Clopper Pearson confidence intervals on the expected proportion have been generated using SAS 9.4.

95% Confidence Intervals								
Objective	Measure	Sample Size	Proportion Estimate	Expected Observed Count	95% LCL	95% UCL		
Primary	# Adverse Events per number of patients	30	0	0	0	0.116		
Intent to Treat	# Adverse Events per number of patients	36	0	0	0	0.097		
Secondary	Compliance	30	0.97	29	0.828	0.999		
Secondary	Withdrawal	36	0.166	6	0.064	0.328		

